7.4 Dose Limiting Toxicity (DLT)

DLT is defined as any of the following possibly, probably, or definitely due to study therapy, assessed during the first 2 cycles [56 days]:

- Any death not clearly due to the underlying disease or extraneous causes
- Non- hematologic toxicity
 - Grade 3 or higher non-hematologic toxicity, Grade 3 diarrhea will be considered a DLT only if it lasts \geq 2 days despite prophylaxis and optimal standard medication and medical management.

- Grade 2 diarrhea lasting \geq 5 days despite prophylaxis and optimal standard medical management
- Pulmonary toxicity
 - Any grade of pneumonitis or ILD confirmed not attributable to infection or another etiology.
- Hy's Law case, defined as a patient meeting all of the following criteria:
 - ALT or AST \geq 3 x Upper Limit of Normal (ULN)
 - Total bilirubin >2 x ULN
 - Little or no evidence of cholestasis (alkaline phosphatase <2 x ULN)
 - No other identified explanation for the injury (such as hepatitis A, B, C, or other viral hepatic injury, alcohol ingestion, congestive heart failure).
- Neutropenic fever, defined as per CTCAE version 5.0:
ANC $<1000/\text{mm}^3$ and a single temperature of >38.3 degrees C (101 degrees F) or a sustained temperature of $>=38$ degrees C (100.4 degrees F) for more than one hour.
- Hematologic toxicity
 - Grade 4 neutropenia or thrombocytopenia >7 days
 - Grade 3 thrombocytopenia with bleeding
 - Grade 4 anemia

The targeted maximum DLT rate is 25%, and we will enroll patients in cohorts of size 3.

Table 4. Capmatinib and Neratinib overlapping toxicities

SOC	Capmatinib toxicity (Ref: CDS)	Neratinib toxicity (Ref: USPI and SmPC)
Congenital, familial and genetic disorders	Embryo-Fetal Toxicity	Embryo-Fetal Toxicity
Gastrointestinal disorders	Diarrhoea	Diarrhoea
	Vomiting	Vomiting
	Nausea	Nausea
	Constipation	Abdominal pain*
	Amylase increased	Stomatitis**
	Lipase increased	Dyspepsia
	Acute pancreatitis	Abdominal distension
		Dry mouth

General disorders and administration site conditions	Fatigue ¹	Fatigue
	Weight decreased	Weight decreased
	Back pain	
	Oedema peripheral ²	
	Non-cardiac chest pain ³	
	Pyrexia ⁴	
Hepatobiliary disorders	Alanine aminotransferase increased	Alanine aminotransferase increased
	Aspartate aminotransferase increased	Aspartate aminotransferase increased
	Blood bilirubin increased	Blood bilirubin increased
	Hypoalbuminemia	
Infections and infestations	Cellulitis	Urinary tract infection
Metabolism and nutrition disorders	Decreased appetite	Decreased appetite
	Hyponatremia	Dehydration
	Hypophosphataemia	
Respiratory, thoracic and mediastinal disorders	Pneumonitis/ILD	Epistaxis
	Dyspnoea	
	Cough	
Skin and subcutaneous tissue disorders	Urticaria	Rash ***
	Pruritus ⁵	Dry skin
		Nail Disorder****
		Skin fissures
Renal and urinary disorders	Blood creatinine increased	Blood creatinine increased
	Acute kidney injury ⁶	Renal failure
Musculoskeletal and Connective Tissue Disorders		Muscle spasms

¹Includes fatigue and asthenia²Includes peripheral swelling, oedema peripheral, and fluid overload³Includes chest discomfort, musculoskeletal chest pain, non-cardiac chest pain, and chest pain⁴Includes pyrexia and body temperature increased⁵Includes pruritus, pruritus allergic, and pruritus generalized⁶Includes acute kidney injury and renal failure.

* Includes abdominal pain, abdominal pain upper, and abdominal pain lower

** Includes stomatitis, aphthous stomatitis, mouth ulceration, oral mucosal blistering, mucosal inflammation, oropharyngeal pain, oral pain, glossodynia, glossitis, and cheilitis

*** Includes rash, rash erythematous, rash follicular, rash generalized, rash pruritic, rash pustular, rash maculo-papular, rash papular, dermatitis, dermatitis acneiform, and toxic skin eruption

**** Includes nail disorder, paronychia, onychoclasia, nail discoloration, nail toxicity, nail growth abnormal, and nail dystrophy

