6.0 Eligibility Criteria

6.1 Inclusion Criteria

1. Signed Informed Consent Form (ICF) and comply with the requirements of the study protocol
2. Age \geq 18 years.
3. ECOG performance status 0-1
4. Confirmed diagnosis of metastatic breast cancer or inflammatory breast cancer according to international consensus criteria³⁰:
 - Onset: Rapid onset of breast erythema, edema, and/or peau d'orange, and/or warm breast, with or without an underlying breast mass
 - Duration: History of such findings no more than 6 months
 - Extent: Erythema occupying at least 1/3 of whole breast
 - Pathology: Pathologic confirmation of invasive carcinoma
5. Patients who have metastatic disease which is not amenable to curative treatment with available local and systemic therapy. Patients must have received at least 1 line or up to 6 lines of therapy in the metastatic setting with at least 2 weeks washout period before the initiation of study treatment.
 - i. Unless a contraindication to therapy exists, patients with ER+ breast cancer must have received prior endocrine therapy combined with a CDK4/6 inhibitor, patients with *BRCA1* or *BRCA2* mutations must have received prior PARP inhibitor, and patients with PD-L1+ triple negative breast cancer must have received prior immunotherapy.
 - ii. Patients with HER2-positive disease must have received at least 2 regimens of anti-HER2 therapy in metastatic setting.

6. For Phase Ib, any ER, PR, and HER2 status, For Phase 2, HER2-negative per ASCO/CAP guidelines and any ER and PR status.

7. For Phase II only, Patients with measurable disease according to the Response Evaluation Criteria in Solid Tumor (RECIST, v1.1) (local or distant) and at least one metastatic lesion amenable for biopsy (core or punch)

NOTE:

Measurable disease: Measurable lesions are defined as those that can be accurately measured in at least one-dimension (longest diameter to be recorded) as ≥ 20 mm by chest X-ray, ≥ 10 mm by computed tomography (CT) scan, ≥ 10 mm with calipers by clinical exam.

Measurable malignant lymph nodes: To be considered pathologically enlarged and measurable, a lymph node must be ≥ 15 mm in short axis when assessed by CT scan.

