Non-measurable disease: All other lesions (or sites of disease), including small lesions, are considered non-measurable. Bone lesions, leptomeningeal disease, ascites, pleural/pericardial effusions, lymphangitis, cutis/pulmonitis, inflammatory breast disease, and abdominal masses [not followed by CT or magnetic resonance imaging (MRI)] are considered non-measurable.

8. Left Ventricular Ejection Fraction $\geq 50\%$ measured by MUGA scan or Echocardiogram.

9. Abnormal HER-family and c-Met signaling activity based on CELsignia MP Test results (for phase II patients only).

10. Participants must have adequate organ function including the following laboratory values at the screening visit. Screening must occur within 28 days prior to the first dose of study drug. Screening samples for hematology and serum chemistries must be drawn within 14 days prior to the first dose of study drug:

- Absolute neutrophil count (ANC) $\geq 1.5 \times 10^9/L$ without growth factor support
- Platelets (PLT) $\geq 75 \times 10^9/L$
- Hemoglobin (Hgb) $\geq 9 \text{ g/dL}$
- Calculated creatinine clearance (using Cockcroft-Gault formula) $\geq 45 \text{ mL/min}$
- Total bilirubin (TBIL) $\leq \text{ULN}$ (upper limit of normal) with the following exception: Patients with known Gilbert disease who have serum bilirubin level $\leq 3 \times \text{ULN}$ may be enrolled.
- Aspartate transaminase (AST) $\leq 3 \times \text{ULN}$, except for participants with liver metastasis, who may only be included if AST $\leq 5 \times \text{ULN}$
- Alanine transaminase (ALT) $\leq 3 \times \text{ULN}$, except for participants with liver metastasis, who may only be included if ALT $\leq 5 \times \text{ULN}$
- Alkaline phosphatase (ALP) $\leq 5.0 \times \text{ULN}$

- Asymptomatic serum amylase \leq grade 2. Participants with grade 1 or grade 2 serum amylase at the beginning of the study must be confirmed to have no signs and/or symptoms suggesting pancreatitis or pancreatic injury (e.g., elevated P-amylase, abnormal imaging findings of pancreas, etc.)
- Serum lipase \leq ULN

11. Willing and able to comply with scheduled visits, treatment plan and laboratory tests. Patients who are cognitively impaired who may not be able to comply with the oral study medication schedule are excluded.

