Grade 1 (> ULN - 1.5 x ULN)	Maintain dose level
Grade 2 (> 1.5 - 3.0 x ULN)	Omit dose until resolved to ≤ grade 1 or baseline, then resume treatment at the same dose level.
Grade 3 (> 3.0 - 6.0 x ULN)	Omit dose until resolved to ≤ grade 1 or baseline, then resume treatment at ↓ 1 dose level.
Grade 4 (> 6.0 x ULN)	Permanently discontinue participant from capmatinib treatment
HEPATIC	
Isolated Total Bilirubin elevation*	
Grade 1 (> ULN - 1.5 x ULN)	Maintain dose level

Grade 2 ($> 1.5 - 3.0 \times \text{ULN}$)	Omit dose until resolved to \leq grade 1, then If resolved in ≤ 7 days, maintain dose level. If resolved in > 7 days, $\downarrow 1$ dose level
Grade 3 ($> 3.0 - 10.0 \times \text{ULN}$)	Omit dose until resolved to \leq grade 1, then If resolved in ≤ 7 days, $\downarrow 1$ dose level If resolved in > 7 days, permanently discontinue participant from capmatinib treatment
Grade 4 ($> 10.0 \times \text{ULN}$)	Mandatory: Permanently discontinue participant from capmatinib treatment
Isolated AST or ALT elevation	
Grade 1 ($> \text{ULN} - 3 \times \text{ULN}$)	Maintain dose level
Grade 2 ($> 3.0 - 5.0 \times \text{ULN}$)	Maintain dose level
Grade 3 ($> 5.0 - 20.0 \times \text{ULN}$)	Omit dose until resolved to \leq grade 1 (or \leq grade 2 if grade 2 elevation at baseline) then If resolved in ≤ 7 days, then resume treatment at the same dose level If resolved in > 7 days, resume treatment at $\downarrow 1$ dose level
Grade 4 ($> 20.0 \times \text{ULN}$)	Mandatory: Permanently discontinue participant from capmatinib treatment
Combined elevations of AST or ALT and Total Bilirubin ^{b,c,d}	
For participants with normal baseline ALT and AST and total bilirubin value: AST or ALT $> 3.0 \times \text{ULN}$ combined with total bilirubin $> 2.0 \times \text{ULN}$ without evidence of cholestasis or hemolysis OR For participants with elevated baseline AST or ALT or total bilirubin value: [AST or ALT $> 3 \times \text{baseline}$] OR [AST or ALT $> 8.0 \times \text{ULN}$], whichever is lower, combined with [total bilirubin $> 2 \times \text{baseline}$ AND $> 2.0 \times \text{ULN}$] without evidence of cholestasis or hemolysis	Mandatory: Permanently discontinue participant from capmatinib treatment
METABOLIC	
Amylase and/or lipase elevation	
Grade 1 ($> \text{ULN} - 1.5 \times \text{ULN}$)	Maintain dose level
Grade 2 ($> 1.5 - 2.0 \times \text{ULN}; > 2.0 - 5.0 \times \text{ULN}$ and asymptomatic)	Maintain dose level

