Grade 3	
Omit dose until resolved to \leq grade 1, then:
 
If resolved in \leq 7 days, resume treatment at same dose level
 
If resolved in $>$ 7 days, resume treatment at \downarrow 1 dose level

Peripheral edema	
Grade 1 or 2	Maintain dose level.
Grade 3	Omit dose until resolved to \leq Grade 1, then \downarrow 1 dose level
Grade 4	Permanently discontinue capmatinib
Other adverse events	
Grade 1 or 2	
Maintain dose level, consider to initiate appropriate support medication.
 
For any intolerable grade 2 (e.g. limiting instrumental ADL), consider omitting the dose until resolved to \leq grade 1, then then restart either at same dose or \downarrow 1 dose level.

Grade 3	Omit dose until resolved to \leq grade 1, then \downarrow 1 dose level
Grade 4	Permanently discontinue capmatinib

All dose modifications should be based on the worst preceding toxicity.
 
a Common Toxicity Criteria for Adverse Events (CTCAE version 5.0).
 
b “Combined” defined as: total bilirubin increase to the defined threshold concurrently with ALT/AST increase to the defined threshold
 
c “Cholestasis” defined as: ALP elevation ($>$ 2.0 x ULN and R value (ALT/ALP in x ULN) $<$ 2.0) in participants without bone metastases, or elevation of ALP liver fraction in participants with bone metastases
 
d If combined elevations of AST or ALT and total bilirubin do not meet the defined thresholds, please follow the instructions for isolated elevation of total bilirubin and isolated elevation of AST/ALT, and take a conservative action based on the degree of the elevations (e.g. discontinue treatment at the situation when omit dose is needed for one parameter and discontinue treatment is required for another parameter). After all elevations resolve to the defined thresholds that allow treatment re-initiation, re-start the treatment either at the same dose or at one dose lower if meeting a criterion for dose reduction
	

* Note: If total bilirubin $> 3.0 \times$ ULN is due to the indirect (non-conjugated) component only, and hemolysis as the etiology has been ruled out as per institutional guidelines (e.g., review of peripheral blood smear and haptoglobin determination), then \downarrow 1 dose level and continue treatment at the discretion of the investigator.

** Note: antidiarrheal medication is recommended at the first sign of abdominal cramping, loose stools or overt diarrhea

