Combined elevations in ALT and/or AST with concurrent total bilirubin increase, in the absence of cholestasis or hemolysis	
Combined elevations of AST or ALT and total bilirubin:
 
After discontinuing the participant from capmatinib permanently, repeat LFTs as soon as possible, preferably within 48 hr from awareness of the abnormal results, then with weekly monitoring of LFTs, or more frequently if clinically indicated, until AST, ALT, or bilirubin have resolved to baseline or stabilization over 4 weeks.
 
Core LFTs consist of ALT, AST, GGT, total bilirubin (fractionated [direct and indirect], if total bilirubin $> 2.0 \times$ ULN), and alkaline phosphatase (fractionated [quantification of isoforms], if alkaline phosphatase $> 2.0 \times$ ULN.)

METABOLIC	
Asymptomatic amylase or lipase \geq CTCAE grade 3	
Test weekly (or more frequently) until \leq CTCAE grade 2.
 
A CT scan or equivalent imaging procedure to assess the pancreas, liver, and gallbladder is recommended within 7 days of the first occurrence of any \geq CTCAE grade 3 result, to exclude disease progression or potential other liver or pancreatic disease.

CARDIAC	
\geq CTCAE grade 3	Test weekly (or more frequently) until \leq CTCAE grade 2.
QTcF \geq 501 ms (CTCAE grade 3)	
When QTcF \geq 501 ms (CTCAE grade 3), perform the following:
 
Perform an analysis of serum potassium, calcium, phosphorus, and magnesium, and if below lower limit of normal, correct with supplements to within normal limits.
 
Review concomitant medication usage for the potential to prolong the QT-interval.
 
Check compliance with correct dose and administration of capmatinib.
 
Perform a repeat ECG within one hour of the first QTcF of \geq 501 ms.
 
If QTcF remains \geq 501 ms, repeat ECG as clinically indicated, but at least once daily until the QTcF returns to < 501 ms.
 
Repeat ECGs 7 days and 14 days (and then every 21 days) after dose resumption for all participants who had therapy interrupted due to QTcF \geq 501 ms.
 
If QTcF of \geq 501 ms recurs, repeat ECGs as described above.
 
Notes:
 
Call the study's central ECG review laboratory immediately and request an immediate manual read of the ECG”

TOXICITY	FOLLOW-UP EVALUATION
	The investigator should contact the Novartis Medical Lead or designee regarding any questions that arise if a participant with QTcF prolongation should be maintained on study.
GASTROINTESTINAL	

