Perform relevant examinations (Ultrasound or MRI, ERCP) as appropriate, to rule out an extrahepatic cause of cholestasis. Cholestasis (is defined as an ALP elevation $>$ 2.0 x ULN with R value $<$ 2 in participants without bone metastases, or elevation of the liver-specific ALP isoenzyme in participants with bone metastases).

Note: The R value is calculated by dividing the ALT by the ALP, using multiples of the ULN for both values. It denotes whether the relative pattern of ALT and/or ALP elevation is due to cholestatic ($R \leq 2$), hepatocellular ($R \geq 5$), or mixed ($R > 2$ and < 5) liver injury. In clinical situations where it is suspected that ALP elevations are from an extrahepatic source, the GGT can be used if available. GGT may be less specific than ALP as a marker of cholestatic injury, since GGT can also be elevated by enzyme induction or by ethanol consumption. It is more sensitive than ALP for detecting bile duct injury (livertox.nih.gov/rucam.html).

Table 17 provides guidance on specific clinical and diagnostic assessments which can be performed to rule out possible alternative causes of observed LFT abnormalities.

Table 17. Clinical And Diagnostic Assessments for LFT Abnormalities

Disease	Assessment
Hepatitis A, B, C, E	IgM anti-HAV; HBsAg, IgM & IgG anti-HBc, HBV DNA; anti-HCV, HCV RNA, IgM & IgG anti-HEV, HEV RNA
CMV, HSV, EBV infection	IgM & IgG anti-CMV, IgM & IgG anti-HSV; IgM & IgG anti-EBV
Autoimmune hepatitis	ANA & ASMA titers, total IgM, IgG, IgE, IgA
Alcoholic hepatitis	Ethanol history, GGT, MCV, CD-transferrin
Nonalcoholic steatohepatitis	Ultrasound or MRI
Hypoxic/ischemic hepatopathy	Medical history: acute or chronic CHF, hypotension, hypoxia, hepatic venous occlusion. Ultrasound or MRI.
Biliary tract disease	Ultrasound or MRI, ERCP as appropriate.
Wilson disease (if <40 yrs old)	Ceruloplasmin
Hemochromatosis	Ferritin, transferrin
Alpha-1-antitrypsin deficiency	Alpha-1-antitrypsin

Other causes should also be considered based upon participants' medical history (hyperthyroidism / thyrotoxic hepatitis – T3, T4, TSH; CVD / ischemic hepatitis – ECG, prior hypotensive episodes; T1D / glycogenic hepatitis).

Obtain PK sample to determine exposure to study treatment and metabolites.

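### The Hy's Law DLT item in Section 7.4 makes no allowance for bone-origin alkaline phosphatase, so a drug-related liver event that ends capmatinib can go uncounted in Phase Ib dose finding

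*Combined protocol and SAP*

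**What the plan says.** Section 7.4 makes a Hy's Law case a DLT only when four criteria hold together: ALT or AST at least 3 x ULN, total bilirubin above 2 x ULN, no other identified explanation, and "Little or no evidence of cholestasis (alkaline phosphatase <2 x ULN"). The ALP limit applies to the total value. The only other item likely to catch a liver laboratory event is Grade 3 or higher non-hematologic toxicity.

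Elsewhere the protocol defines cholestasis differently. In Section 10.5.2, the Table 15 row headed "Combined elevations of AST or ALT and Total Bilirubin" mandates permanent discontinuation of capmatinib when cholestasis and hemolysis are absent. Footnote c defines cholestasis as ALP above 2.0 x ULN with R (ALT/ALP, each in multiples of ULN) below 2.0 in patients without bone metastases, "or elevation of ALP liver fraction in participants with bone metastases". Section 10.5.3 repeats this: "or elevation of the liver-specific ALP isoenzyme in participants with bone metastases". For these same combined elevations, the core tests in Table 16 include "alkaline phosphatase (fractionated [quantification of isoforms], if alkaline phosphatase" is above 2.0 x ULN.

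On who can enter, Section 6.1 item 10 allows ALP up to 5.0 x ULN whatever its source. Item 7 begins "For Phase II only, Patients with measurable disease according to the Response Evaluation Criteria in Solid Tumor", so Phase Ib does not require measurable disease. The note to that item lists as non-measurable "Bone lesions, leptomeningeal disease, ascites" and other sites. Section 6.2 also provides for recent palliative radiotherapy to bone metastases.

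Section 7.3 requires 80% of scheduled doses of each drug for DLT evaluability, but counts any DLT whatever the number of doses taken. In Section 13.1, Table 18 and the isotonic MTD selection use DLT counts among evaluable patients.

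**The concern.** The ALP criterion is there to keep cholestatic injury out of the Hy's Law item. In a patient whose ALP is raised by bone disease, it can instead exclude an injury that the protocol's own definition calls non-cholestatic. Table 4 lists raised ALT, AST and bilirubin for both drugs, and Section 8.2.2 advises caution when capmatinib is combined with hepatotoxic agents, so this is a toxicity that dose finding should register.

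At stake is the count that drives escalation. The event may drop out of the numerator alone or, after an early stop, out of numerator and denominator together. With cohorts of 3, one patient can decide the next step.

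**Working it through.** **Plan's own boundaries.** With target 0.25 and alternatives of 0.6 and 1.4 times the target (0.15 and 0.35; an assumption, since Appendix 1 says only that defaults are used):

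- Escalation: ln(0.85/0.75) / ln[(0.25 x 0.85)/(0.15 x 0.75)] = 0.1968 (plan: 0.197).
- De-escalation: ln(0.75/0.65) / ln[(0.35 x 0.75)/(0.25 x 0.65)] = 0.2984 (plan: 0.298).

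These reproduce Table 18, apart from the stated 3+3 override at n = 3.

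**The gap.** Take a patient with bone metastases, normal baseline AST, ALT and bilirubin, ALP 3 x ULN and a normal liver fraction. On day 20, ALT is 4 x ULN and bilirubin 2.5 x ULN, drug-related, with no hemolysis and no other explanation.

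| Rule | Result |
|---|---|
| Table 15 grades | ALT Grade 2 (>3-5), bilirubin Grade 2 (>1.5-3) |
| 7.4 Grade 3 item | not met |
| 7.4 Hy's Law item | fails on ALP alone (3 is not <2) |
| Table 15 footnote c | no cholestasis |
| Table 15 action | mandatory permanent capmatinib stop |

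With ALP 1.5 x ULN the same patient is a Hy's Law DLT. With ALT 6 x ULN the Grade 3 item applies whatever the ALP. The gap is therefore confined to ALT/AST of 3-5, bilirubin above 2 and up to 3, and ALP of at least 2 x ULN.

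**Evaluability.** Capmatinib twice daily for 56 days is 112 doses, and 0.8 x 112 = 89.6, so 90 doses (45 full days) are needed. Forty-four days give 88/112 = 78.6%; 45 days give 90/112 = 80.4%. A stop on day 20 leaves at most 40/112 = 36%, so the patient is non-evaluable. A stop after day 45 leaves the patient evaluable without a DLT.

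**Effect of one early-stop event in the first cohort at a dose.** Let p be the true DLT rate and X the number of DLTs in the other two patients. If counted, the cohort has X + 1 DLTs out of 3. If uncounted and replaced, it has X plus the replacement's result, so the count differs only when the replacement has no DLT (probability 1-p). At n = 3 the Table 18 actions are 0 escalate, 1 stay, 2 de-escalate, 3 eliminate. Elimination is treated as distinct from de-escalation because it bars return to the dose.

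- Middle dose: every one-step difference changes the action, so 1-p.
- Highest dose (Section 13.1 step 2e): 0/3 and 1/3 both mean staying, so (1-p)[1-(1-p)^2].
- Lowest dose (step 2d): 1/3 and 2/3 both mean staying, so (1-p)[(1-p)^2 + p^2].

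| True DLT rate | Middle | Highest | Lowest |
|---|---|---|---|
| 10% | 90% | 17% | 74% |
| 25% | 75% | 33% | 47% |
| 40% | 60% | 38% | 31% |

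At a middle dose, the specific change from stay (1/3) to escalate (0/3) has probability (1-p)^3 = 73%, 42% and 22%.

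**Frequency.** The documents give none. Purely as assumptions, per-patient rates of 0.05%, 0.3% and 1% give 1-(1-q)^18 = 0.9%, 5.3% and 16.5% for at least one event among 18 patients.

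**The case against.** The strongest reply is that the individual patient is already protected. Capmatinib stops for good, Section 10.5.3 makes confirmed cases reportable as SAEs, and the IND Medical Monitor approves every dose change. That stands, but none of these steps puts the case into the Table 18 count.

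A second reply is that the case might still become a DLT if the syndrome is recorded instead of the laboratory values (Section 12.1.4) and graded 3 or higher. That is possible. No rule requires it, and the general scale in Section 12.1.3, for events outside CTCAE, describes Grade 3 as discomfort that interrupts daily activity, which an asymptomatic laboratory rise does not fit. Whether CTCAE covers the recorded term cannot be checked from the documents.

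Third, a DLT list and a single-drug dose-modification table serve different purposes and need not match. This is correct, and it limits the point. A reader might infer that every mandatory permanent stop should be a DLT, or that Section 7.4 should adopt footnote c in full, including its R-value limb. The documents do not support either. With ALT at most 5 and ALP at least 2 x ULN, R cannot exceed 5/2 = 2.5. Section 10.5.3 calls R up to 2 cholestatic, between 2 and 5 mixed, and 5 or more hepatocellular. Without a bone source, such cases are therefore mixed at best (ALT 4.8 and ALP 2.2 give R = 2.18), and at ALT 4.4 and ALP 2.2, R is exactly 2.0, cholestatic on that scale. Section 7.4 reasonably leaves them out.

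Finally, the conditional probabilities would be the same for any uncounted DLT. They show the leverage of one patient, not how often this event occurs.

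**Conclusion.** The point holds for patients with bone metastases only. Section 7.4 can exclude a drug-related, non-cholestatic liver event from the DLT count because of bone-origin ALP, while Table 15 ends capmatinib for the same event.

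The leverage figures assume that the event has occurred in the first cohort at a dose, that the non-evaluable patient is replaced, and that neighbouring doses remain open. The Section 13.2 reporting schedule, by sets of 3 evaluable patients, suggests replacement, but no explicit rule is given. The middle-dose figures should not be read as applying at every dose.

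A reader might also infer that the dose-finding design is invalid or that patients go unprotected. Neither follows: the laboratory window is narrow, the frequency is unknown and probably low, and other safeguards act. This is a cheap improvement to the DLT definition.

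**What to change.** Reword the ALP criterion in Section 7.4 as: *alkaline phosphatase <2 x ULN, or, in participants with bone metastases and alkaline phosphatase >=2 x ULN, no elevation of the ALP liver fraction*. Leave the other Hy's Law criteria, and the ALP criterion for patients without bone metastases, as they are.

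Check, with bilirubin 2.5 x ULN and ALT 4 x ULN unless stated:

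- Bone metastases, ALP 3, normal liver fraction: becomes a DLT.
- Bone metastases, ALP 1.5, raised liver fraction: remains a DLT.
- Bone metastases, ALP 3, raised liver fraction: remains outside the item.
- No bone metastases, ALP 3 (R = 4/3 = 1.33): remains outside the item.
- No bone metastases, ALT 4.8, ALP 2.2 (R = 2.18): remains outside the item.

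No existing DLT is lost. The Section 7.3 sentence on counting DLTs regardless of doses then keeps the first case in the Table 18 count even after an early stop.

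The cost is one phrase. Table 16 already requires ALP fractionation above 2.0 x ULN, so only a value of exactly 2.0 x ULN would need an extra test. The downsides are possibly slightly more DLTs and the need to have the fraction back before the cohort summary is submitted.
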